### **6.3.1 Handling of study treatment and other treatment**

#### **6.3.1.1 Handling of study treatment**

Study treatment must be received by a designated person at the study site, handled and stored safely and properly and kept in a secured location to which only the investigator and designated site personnel have access. Upon receipt, all study treatment must be stored according to the instructions specified on the treatment labels.

Clinical supplies are to be dispensed only in accordance with the protocol. Technical complaints are to be reported to the respective Novartis CO Quality Assurance.

Medication labels will be in the local language and comply with the legal requirements of each country. They will include storage conditions for the study treatment but no information about the participant except for the medication number.

Participants in Cohort 1 will be asked to return all unused study treatment and packaging at the end of the study or at the time of discontinuation of study treatment.

The investigator must maintain an accurate record of the shipment and dispensing of study treatment in a drug accountability log. Monitoring of drug accountability will be performed by monitors during site visits or remotely and at the completion of the trial.

At the conclusion of the study, the site may destroy and document destruction of unused study treatment, drug labels and packaging as appropriate in compliance with site processes,

monitoring processes, and per local regulation/guidelines after approval from the Novartis Clinical Lead. Otherwise, the investigator will return all unused study treatment, packaging, drug labels, and a copy of the completed drug accountability log to the Novartis or its agent.

The study treatment and all required clinical study supplies will be distributed direct to the participant utilizing an extension of the IND for compliance purposes.

### **6.3.2 Instruction for prescribing and taking study treatment**

#### **COVID-19 mRNA vaccine**

The vaccine should be obtained through the HCP (private insurance) or appropriate federal, state or local program.

#### **Participants in Cohort 1**

Ofatumumab will be provided in an auto injector for subcutaneous administration containing 20 mg ofatumumab (20 mg/0.4 ml). Treatment should be administered after study assessments have been completed for the visit.

Cohort 1 should receive their first loading dose of ofatumumab at Visit 4 which should be held 2 weeks after receiving their 2nd COVID-19 vaccine dose.

Site staff should remove the study treatment from the refrigerator and allow the auto injector pen to reach room temperature in their unopened box (approximately 15-30 minutes) before self-injection by the participant. Used syringes should be disposed of immediately after use in a sharps container.

A different body site (front of thighs, lower abdomen) should be chosen each time a dose is administered to reduce the risk of an injection-site reaction; investigator/qualified site staff/caregiver can also inject the study treatment in the outer upper arms. Each new injection should be given at least one inch from the previously used site. If administration is in the abdomen, the 2-inch area around navel should be avoided. Study treatment should also not be injected into areas where the skin is tender, bruised, red, or hard, or where the participant has scars or stretch mark

As participants must self-administer ofatumumab, site personnel will provide training on the correct procedure for injection technique of the ofatumumab subcutaneous injections to enable the participant and/or a caregiver to administer from home in-between scheduled office visits. Documentation of the participant or caregiver understanding the correct administration procedure must be documented in the source document. Participants will be instructed to contact the investigator/site staff prior to self-administration at home if they are experiencing any AE/SAEs or have any concerns.

Site personnel will make remote contact with participants in Cohort 1 on/around the time of the 2nd loading dose to query about any new or worsening symptoms warranting an unscheduled visit, compliance with study treatment, injection reactions, and compliance with contraception requirements when applicable.

Additional remote contacts should be conducted on/around the time participants are due to administer treatment at home. The method of contact with each participant can be the personal

preference of the individual between telephone contacts, email contact or text messages, however, the site staff must be able to provide suitable source documentation of each contact regardless of the method of contact.

Participants will be asked to complete a participant diary to record doses of home administrations of ofatumumab.

All kits of study treatment assigned by the IRT will be recorded in the IRT system.

## **Participants in Cohort 2**

Upon enrollment, participants already receiving prescribed ofatumumab will continue to take prescribed treatment as per their current dosing schedule.

Participants will be asked to complete a participant diary to record doses of ofatumumab administered while in the study.

## **Participants in Cohort 3**

Upon enrollment, participants in Cohort 3 will continue to take their interferon or glatiramer acetate as per their current dosing schedule.

Participants will be asked to complete a participant diary to record doses of their interferon or glatiramer acetate taken during the study.

## **Participants in Cohort 4**

Upon enrollment, participants will continue to take prescribed ofatumumab treatment as per their current dosing schedule.

Participants will be asked to complete a participant diary to record doses of ofatumumab administered while in the study.

## **Participants in Cohort 5**

Upon enrollment, participants will continue their prescribed interferon or glatiramer acetate treatment as per their current dosing schedule.

Participants will be asked to complete a participant diary to record doses of ofatumumab administered while in the study.

## **Participants in Cohort 6**

Upon enrollment, participants will continue their prescribed ofatumumab treatment as per their current dosing schedule.

Participants will be asked to complete a participant diary to record doses of ofatumumab administered while in the study.

**Table 6-3 Dose and treatment schedule**

	Investigational Drug	Frequency and/or Regimen
Cohort 1	OMB157 20mg/0.4mL	Day 36, 43, 50, 64 and monthly thereafter for participants that receive the Pfizer vaccine. Day 43, 50, 57, 71 and monthly thereafter for participants that receive the Moderna vaccine.
Cohort 2	OMB157 20mg/0.4mL	Monthly as prescribed
Cohort 3	Interferon or glatiramer acetate	As prescribed
Cohort 4	OMB157 20mg/0.4mL	As prescribed
Cohort 5	Interferon or glatiramer acetate	As prescribed
Cohort 6	OMB157 20mg/0.4mL	As prescribed

## **6.4 Participant numbering, treatment assignment, randomization**

### **6.4.1 Participant numbering**

Each participant is identified in the study by a Participant Number (Participant No.), that is assigned when the participant is enrolled for screening and is retained for the participant throughout his/her participation in the trial. A new Participant No. will be assigned at every subsequent enrollment if the participant is re-screened. The Participant No. consists of the Center Number (Center No.) (as assigned by Novartis to the investigative site) with a sequential participant number suffixed to it, so that each participant's participation is numbered uniquely across the entire database. Upon signing the informed consent form, the participant is assigned to the next sequential Participant No. available.

At the Screening Visit (Visit 1/Day -7), the Investigator or his/her staff will contact the Interactive Response Technology (IRT) system and provide the assigned participant study identification number along with the requested identifying information to register the participant into IRT. The site must use the eCRF with the matching participant number from the electronic data capture (EDC) system to enter data.

Once assigned to a participant, a participant number will not be reused. If a participant fails to be enrolled for any reason, the IRT system must be notified within 2 days and the reason for not being enrolled will be entered on the Screening Phase Disposition Form and the appropriate eCRF(s) pages should also be completed.

#### **6.4.1.1 Treatment assignment, randomization**

No randomization will be performed in this study. The assignment of a participant to a cohort will be determined by inclusion/exclusion criteria.

An IRT system will be used to track participant visits and status. IRT will also be used to dispense treatment to Cohort 1 as indicated in the assessment schedules in [Table 8-1](#) and [Table 8-2](#).

At dosing visits, the system will specify unique medication numbers that will correspond to open-label treatment to be dispensed.

## **6.5 Treatment blinding**

Not applicable.

## **6.6 Dose escalation and dose modification**

Dose adjustments and/or interruptions are not permitted.

## **6.7 Additional treatment guidance**

Not applicable.

### **6.7.1 Treatment compliance**

Participant compliance with treatment should be at least 80%. The Investigator and/or study personnel will counsel the participant if compliance is below 80%. The investigator must promote compliance by instructing the participant to take the study treatment exactly as prescribed and by stating that compliance is necessary for the participant's safety and the validity of the study. The participant must also be instructed to contact the investigator if he/she is unable for any reason to take the study treatment as prescribed. Compliance will be assessed by the investigator and/or study personnel at each visit using information provided by the participant. This information should be captured in the source document at each visit for Cohort 1 and in the eCRF for Cohorts 2, 3, 4, 5 and 6.

All study treatment dispensed and returned must be recorded in the Drug Accountability Log.

### **6.7.2 Emergency breaking of assigned treatment code**

Since this study is open-label, emergency breaking of assigned treatment codes is not applicable.

## **7 Informed consent procedures**

Eligible participants may only be included in the study after providing (witnessed, where required by law or regulation), IRB-approved informed consent.

Informed consent must be obtained before conducting any study-specific procedures (e.g. all of the procedures described in the protocol). The process of obtaining informed consent must be documented in the participant source documents.

Novartis will provide to investigators in a separate document a proposed informed consent form that complies with the ICH E6 Good Clinical Practice (GCP) guidelines and regulatory requirements and is considered appropriate for this study. Any changes to the proposed consent form suggested by the investigator must be agreed by Novartis before submission to the IRB/.

Information about common side effects already known about the investigational treatment can be found in the IB and USPI. This information will be included in the participant informed consent and should be discussed with the participant during the study as needed. Any new information regarding the safety profile of the investigational drug that is identified between IB updates will be communicated as appropriate, for example, via an investigator notification or

an aggregate safety finding. New information might require an update to the informed consent and then must be discussed with the participant.

The following informed consents are included in this study:

- Main study consent, which also included:
  - A subsection that requires a separate signature for the 'Optional Consent for Additional Research' to allow future research on data/samples collected during this study
  - As applicable, Pregnancy Outcomes Reporting Consent for female participants or the female partners of any male participants who took study treatment

Women of childbearing potential must be informed that taking the study treatment may involve unknown risks to the fetus if pregnancy were to occur during the study and agree that in order to participate in the study they must adhere to the contraception requirements.

A copy of the approved version of all consent forms must be provided to Novartis after IRB approval.

As per [Section 4.6](#), during a Public Health emergency as declared by Local or Regional authorities i.e. pandemic, epidemic or natural disaster, that may challenge the ability to obtain a standard written informed consent due to limits that prevent an on-site visit, Investigator may conduct the informed consent discussion remotely (e.g. telephone, videoconference) if allowable by a local Health Authority. Guidance issued by local regulatory bodies on this aspect prevail and must be implemented and appropriately documented (e.g. the presence of an impartial witness, sign/dating separate ICFs by trial participant and person obtaining informed consent, etc.).

## 8 Visit schedule and assessments

The below Assessment Schedules ([Table 8-1](#), [Table 8-2](#), [Table 8-3](#), [Table 8-4](#), [Table 8-5](#) and [Table 8-6](#)) list all assessments with an X when they are performed. All data obtained from these assessments must be supported in the participant's source documentation. The "X" in the table denotes the assessments to be recorded in the clinical database or received electronically from a vendor. The "S" in the table denotes the assessments that are only in the participant's source documentation and do not need to be recorded in the clinical database.

Participants should be seen for all visits/assessments as outlined in the assessment schedules or as close to the designated day/time as possible. The Investigator should promote compliance by instructing the participant to attend the study visits as scheduled and by stating that compliance is necessary for the participant's safety and the validity of the study. Missed or rescheduled visits should not lead to automatic discontinuation. The participant should be instructed to contact the Investigator if he/she is unable for any reason to attend a study visit as scheduled or if he/she is unable for any reason to take the study treatment as prescribed.

Participants who prematurely discontinue the study should be scheduled for the End of Study (EOS) visit within 7 days. At this final visit, all the assessments mentioned under EOS visit should be performed, all dispensed investigational product should be reconciled, and the

adverse event and concomitant medications recorded on the CRF. Participants that prematurely discontinue should also have a remote follow-up safety visit performed 30 days after the EOS visit.

### **Special guidance regarding the scheduling of visits for Cohorts 1, 2 and 3**

- The study site will need to perform Vaccine Status Check-ins (make remote contact with participant) to confirm when the 1st and 2nd COVID-19 vaccinations are scheduled in order to schedule Visit 4.
- The date of the 2nd COVID-19 vaccine dose will determine the date of Visit 4 and all other remaining study visits.
- Visits 2 and 3 should always occur prior to administration of the mRNA vaccine.
- The Visit 4 lab samples should be collected 14 days after a participant has received their 2nd COVID-19 vaccine dose.

### **Home study visits (Cohort 1)**

Home (remote) study visits are planned at Visits 5, 6 and 7 for participants in Cohort 1. To facilitate this, at Visit 4, sufficient study drug can be supplied to the participant to cover all home administrations of study drug until the Visit 8 in-person, clinic visit. Refer to [Section 6.7](#) for additional information.

Participants and/or caregivers trained to administer the ofatumumab subcutaneous injections will need to administer treatment at home study visits. Refer to [Table 8-1](#) and [Table 8-2](#).

The option for a participant to return to the clinic for administration of treatment at Visits 5, 6 and 7 is available if that is his/her preference.

### **Unscheduled visits**

In addition to the scheduled visits, participants may have unscheduled visits due to a MS relapse, an acute illness of undetermined cause, for other reasons, or at the discretion of the Investigator. Data collected during unscheduled visits will be recorded in the unscheduled visits CRF.

**Table 8-1** Assessment schedule for Cohort 1 (Pfizer vaccine)

Period	Screening	Treatment									Follow-up	
Visit Name	Visit 1 Screening	Visit 2 (home visit)	Visit 3 (home visit)	Visit 4 (office visit)	Visit 5 Visit 6 Visit 7 (home visit)	Visit 8 (office visit)	Visit 9 (office visit)	Visit 10 (office visit)	Visit 11/ End of Study – EOS (office visit)	Visit 12 / Safety (remote contact)	Unscheduled	
Day/Week/Month	Day -7	Day 1	Day 22	Day 36	Day 43 Day 50 Day 64	Day 92	Day 202	Day 292	Day 382	Day 412		
Visit Window				+/-3d	+/-3d	+/-3d	+/-3d	+/-3d	+/-3d	+/-3d		
SARS CoV2 qualitative antibody	X			X		X	X	X	X			
Serum Immunoglobulin 	X			X		X	X		X			
CD 19+ B cells	X			X		X	X	X	X			
Biobanked serum sample 	X			X								
Biobanked whole blood sample 	X			X								
Vaccine Administration Form		X	X									
IRT Transaction	X	X	X	X	X	X	X	X	X			
Self-Injection Training				S								

Period	Screening	Treatment									Follow-up	
		Visit 1 Screening	Visit 2 (home visit)	Visit 3 (home visit)	Visit 4 (office visit)	Visit 5 Visit 6 Visit 7 (home visit)	Visit 8 (office visit)	Visit 9 (office visit)	Visit 10 (office visit)	Visit 11/ End of Study – EOS (office visit)		
Visit Name											Visit 12 / Safety (remote contact)	Unscheduled
Day/Week/Month	Day -7	Day 1	Day 22	Day 36	Day 43 Day 50 Day 64	Day 92	Day 202	Day 292	Day 382	Day 412		
Visit Window				+-3d	+-3d	+-3d	+-3d	+-3d	+-3d	+-3d		
Office administration of study drug				X		X						
Dispense study drug for future home administration				X		X	X	X				
Home administration of study drug					X							
Patient Diary/Drug Accountability				X	X	X	X	X	X			
Adverse Events / Serious Adverse Events	X	X	X	X	X	X	X	X	X	S		X
Subject disposition	X									X	S	
Vaccine check-in contacts 		S	S									
Remote check-in 					S						S	

X = assessment to be recorded in the clinical database or received electronically from a vendor

S = assessment to be recorded in the source documentation only

 Serum pregnancy should be performed locally for all sites except those unable to use a local lab. Sites unable to perform locally should send sample to the central lab.

 Participants with lab results within the past 6 months prior to screening will not require labs drawn at screening visit. Local labs should be documented in the source. Participants without lab results from the past 6 months prior to screening will require central labs drawn at the screening visit to be entered into the clinical database.

 Sample will be bio-banked for yet to be identified analyses.

 Vaccine check-ins (remote contacts) by site staff to confirm participant has received the COVID-19 vaccine and to collect any AEs/SAEs.

 Remote contact with participants by site staff. The contact should query about receipt any new AEs or SAEs, changes in con meds and compliance with current treatment. Method of contact can be via telephone, email or text message depending on the preference of each participant.

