**Table 8-2 Assessment schedule for Cohort 1 (Moderna vaccine)**

Period	Screening	Treatment									Follow-up	
		Visit 1 Screening	Visit 2 (home visit)	Visit 3 (home visit)	Visit 4 (office visit)	Visit 5 Visit 6 Visit 7 (home visit)	Visit 8 (office visit)	Visit 9 (office visit)	Visit 10 (office visit)	Visit 11/ End of Study – EOS (office visit)		
Visit Name												
Day/Week/Month	Day -7	Day 1	Day 29	Day 43	Day 50 Day 57 Day 71	Day 99	Day 209	Day 299	Day 389	Day 419		
Visit Window					+/-3d	+/-3d	+/-3d	+/-3d	+/-3d	+/-3d		
Obtain informed consent	X											
Inclusion/exclusion criteria	X											
Demography	X											
Relevant medical history/current medical history	X											
Non-drug therapies and procedures	X	X	X	X	X	X	X	X	X	S	X	
Prior/Concomitant Medications	X	X	X	X	X	X	X	X	X	S	X	
MS Relapse	X	X	X	X	X	X	X	X	X	S	X	
Serum Pregnancy Test 	S								S			

Period	Screening	Treatment									Follow-up	
Visit Name	Visit 1 Screening	Visit 2 (home visit)	Visit 3 (home visit)	Visit 4 (office visit)	Visit 5 Visit 6 Visit 7 (home visit)	Visit 8 (office visit)	Visit 9 (office visit)	Visit 10 (office visit)	Visit 11/ End of Study – EOS (office visit)	Visit 12 / Safety (remote contact)	Unscheduled	
Day/Week/Month	Day -7	Day 1	Day 29	Day 43	Day 50 Day 57 Day 71	Day 99	Day 209	Day 299	Day 389	Day 419		
Visit Window				+/-3d	+/-3d	+/-3d	+/-3d	+/-3d	+/-3d	+/-3d		
Self-Injection Training				S								
Office administration of study drug				X		X						
Dispense study drug for future home administration				X		X	X	X				
Home administration of study drug					X							
Patient Diary/Drug Accountability				X	X	X	X	X	X			
Adverse Events / Serious Adverse Events	X	X	X	X	X	X	X	X	X	S	X	
Subject disposition	X								X	S		
Vaccine check-in contacts 		S	S									
Remote check-in 					S					S		

X = assessment to be recorded in the clinical database or received electronically from a vendor

S = assessment to be recorded in the source documentation only

 Serum pregnancy should be performed locally for all sites except those unable to use a local lab. Sites unable to perform locally should send sample to the central lab.

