**Table 8-3 Assessment schedule for Cohorts 2 and 3 (Pfizer vaccine)**

Period	Screening	Treatment						Follow-up	
Visit Name	Visit 1 Screening	Visit 2	Visit 3	Visit 4	Visit 5	Visit 6	Visit 7/End of Study (EOS)	Visit 8 / Safety	Unscheduled
Day/Week/Month	Day -7	Day 1	Day 22	Day 36	Day 202	Day 292	Day 382	Day 412	
Visit Window				+3d	+/-3d	+/-3d	+/-3d	+/-3d	
Obtain informed consent	X								
Inclusion/exclusion criteria	X								
Demography	X								
Relevant medical history/current medical history	X								
Non-drug therapies and procedures	X	X	X	X	X	X	X	S	X
Prior/Concomitant Medications	X	X	X	X	X	X	X	S	X
MS Relapse	X	X	X	X	X	X	X	S	X
Serum Pregnancy Test 	S						S		

Period	Screening	Treatment						Follow-up	
Visit Name	Visit 1 Screening	Visit 2	Visit 3	Visit 4	Visit 5	Visit 6	Visit 7/End of Study (EOS)	Visit 8 / Safety	Unscheduled
Day/Week/Month	Day -7	Day 1	Day 22	Day 36	Day 202	Day 292	Day 382	Day 412	
Visit Window				+3d	+/-3d	+/-3d	+/-3d	+/-3d	
Hepatitis B virus (HBV) (Cohort 2 only) 	X								
SARS CoV2 qualitative antibody		X	X	X	X	X	X		
Serum Immunoglobulin 	X				X		X		
CD 19+ B cells (Cohort 2 only)	X	X	X	X	X	X	X		
Biobanked serum sample 	X			X					
Biobanked whole blood sample 	X			X					
Vaccine Administration Form		X	X						
IRT Transaction	X	X	X	X	X	X	X		
Drug Accountability		S	S	S	S	S	S		
Adverse Events / Serious Adverse Events	X	X	X	X	X	X	X	S	X
Subject disposition	X						X	S	

X = assessment to be recorded in the clinical database or received electronically from a vendor

S = assessment to be recorded in the source documentation only

 Serum pregnancy should be performed locally for all sites except those unable to use a local lab. Sites unable to perform locally should send sample to the central lab.

 Participants with lab results within the past 6 months prior to screening will not require labs drawn at screening visit. Local labs should be documented in the source. Participants without lab results from the past 6 months prior to screening will require central labs drawn at the screening visit to be entered into the clinical database.

 Sample will be bio-banked for yet to be identified analyses.

 Vaccine check-ins (remote contacts) by site staff to confirm participant has received the COVID-19 vaccine and to collect any AEs/SAEs.

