All adverse events must be treated appropriately. Treatment may include one or more of the following:

- Dose not changed
- Dose Reduced/increased
- Drug interrupted/permanently discontinued

Conditions that were already present at the time of informed consent should be recorded in medical history of the participant.

Adverse events (including lab abnormalities that constitute AEs) should be described using a diagnosis whenever possible, rather than individual underlying signs and symptoms.

Adverse event monitoring should be continued for at least 30 days following the last dose of study treatment.

Once an adverse event is detected, it must be followed until its resolution or until it is judged to be permanent (e.g. continuing at the end of the study), and assessment must be made at each visit (or more frequently, if necessary) of any changes in severity, the suspected relationship to the interventions required to treat it, and the outcome.

Information about adverse drug reactions for the investigational drug can be found in the IB or USPI.

Abnormal laboratory values or test results constitute adverse events only if they fulfill at least one of the following criteria:

- they induce clinical signs or symptoms
- they are considered clinically significant
- they require therapy

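### Non-serious AEs first found or updated at the 30-day safety contact are source-only in all six schedules, with no scheduled route to the clinical database or the AE tables

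*Protocol*

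**What the plan says.** Protocol Section 8 uses two marks in its schedules. An X goes to the clinical database. The legend for the other mark is "S = assessment to be recorded in the source documentation only", and the text of Section 8 says that such items "do not need to be recorded in the clinical database".

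The AE/SAE row carries an X at every scheduled visit up to end of study (EOS) and at unscheduled visits, and an S only at the safety contact. In Table 8-2 (Cohort 1, Moderna) it reads "Adverse Events / Serious Adverse Events X X X X X X X X X S X", and in Table 8-3 (Cohorts 2 and 3, Pfizer) "Adverse Events / Serious Adverse Events X X X X X X X S X". The next-to-last entry in each is the safety contact. The other four tables follow the same pattern.

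On the duration of follow-up, protocol Section 10.1.1 states: "Adverse event monitoring should be continued for at least 30 days following the last dose of study treatment". Section 8 adds: "Participants that prematurely discontinue should also have a remote follow-up safety visit performed 30 days after the EOS visit". The footnote on remote check-ins says that the contact should ask about new AEs and SAEs.

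On reporting, protocol Section 12.5.1 limits the AE tables to events in the on-treatment period but does not define when that period ends. SAP Section 2.7.1 instead tabulates on-study events that begin or get worse from Visit 1 onward, and it gives no end date. Section 10.1.3 gives SAEs a separate 24-hour report to the sponsor's safety group until 30 days after the last study visit.

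**The concern.** AEs and SAEs are a stated secondary endpoint (protocol Table 2-1, SAP Table 1). The protocol schedules a contact to ask about them after EOS, but the schedule does not ask for the answers to be entered. A non-serious AE that first comes to light there, or a change in one already recorded, can stay in the site's notes. The SAP's AE definition would count it, but the analyst would have no record of it.

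SAEs are in a mixed position. They reach the safety group under Section 10.1.3, but the S covers the whole AE/SAE row, so the schedule does not require an SAE found at this contact to enter the clinical database. I found no passage saying that the safety database feeds the SAE tables.

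The gap matters most for participants who leave the study early. For them the 30-day contact is the only scheduled look after EOS, and some of the reasons listed in Section 9.1.1 for stopping treatment are themselves safety events.

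**Working it through.** **Step 1. The AE/SAE row in the six schedules.**

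| Table | Cohorts, vaccine | X at | S at | EOS day | Contact day |
|---|---|---|---|---|---|
| 8-1 | 1, Pfizer | Visits 1-11 | Visit 12 | 382 | 412 |
| 8-2 | 1, Moderna | Visits 1-11 | Visit 12 | 389 | 419 |
| 8-3 | 2-3, Pfizer | Visits 1-7 | Visit 8 | 382 | 412 |
| 8-4 | 2-3, Moderna | Visits 1-7 | Visit 8 | 389 | 419 |
| 8-5 | 4-6, Pfizer | Visits 1-5 | Visit 6 | 382 | 412 |
| 8-6 | 4-6, Moderna | Visits 1-5 | Visit 6 | 389 | 419 |

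Unscheduled visits are X in all six.

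**Step 2. Length of the gap.** 412 − 382 = 30 days and 419 − 389 = 30 days. Both agree with the 30 days in Section 8.

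**Step 3. Cohort 1 completers: how much of the required post-dose window falls after EOS.** Inputs: monthly dosing starts on Day 64 (Pfizer) or Day 71 (Moderna), from Table 6-3. No dose is scheduled at EOS, since Visit 10 dispenses three monthly home doses (Section 6.3). The documents say only monthly, so the interval m is an assumption. For Pfizer:

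- last dose L = 64 + k × m, with k the largest whole number that keeps L below 382
- required monitoring ends on L + 30
- days after EOS = L + 30 − 382

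| m (days) | k | L | L + 30 | Days after EOS | Days up to EOS |
|---|---|---|---|---|---|
| 28 | 11 | 372 | 402 | 20 | 10 |
| 30 | 10 | 364 | 394 | 12 | 18 |
| 30.4 | 10 | 368 | 398 | 16 | 14 |
| 31 | 10 | 374 | 404 | 22 | 8 |

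For Moderna, both the first monthly dose and EOS move by 7 days, so the last two columns are the same. The 8 to 18 days up to EOS are covered by the X at the EOS visit. The 12 to 22 days after it are covered on schedule only by the S contact.

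The range is approximate. Counting from the Day 92 office dose in Table 8-1 gives 92 + 9 × 30 = 362 and 362 + 30 − 382 = 10 days at m = 30, and 92 + 9 × 31 = 371 and 371 + 30 − 382 = 19 days at m = 31; m = 28 stays at 20. A constant 29-day interval from Day 64 would give L = 64 + 10 × 29 = 354 and only 354 + 30 − 382 = 2 days, because the next dose would fall on Day 383, just after EOS. The 3-day visit window moves EOS as well.

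**Step 4. Participants who leave early.** Section 8 puts their EOS visit within 7 days and the safety contact 30 days after it. All 30 days of planned post-EOS follow-up are therefore source-only.

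**Step 5. Completers in Cohorts 2-6.** These are 88 − 22 = 66 of the planned participants. They continue their own prescribed treatment, so EOS is not a last dose. Their 30 days are post-EOS, and no part of them is shown to be required post-dose time.

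**Step 6. Share of follow-up time.** From Day −7 the span is about 412 + 7 = 419 days (Pfizer) or 419 + 7 = 426 days (Moderna). 30/419 = 7.2% and 30/426 = 7.0%. These are shares of calendar time.

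**The case against.** The best defence is that the S is deliberate. In the same column, non-drug therapies, concomitant medications, MS relapse and disposition are also S. The SAP's disposition events stop at end of study. Section 10.1.1 asks for monitoring, which a call written up in source delivers, and it lets an event be closed as permanent if it continues at the end of the study. Under protocol 12.5.1, post-treatment events may lie outside the AE tables by design. SAEs, the events that matter most, have their own route.

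Much of this is fair, and it keeps the point small. It does not remove it. A remote contact is no reason for source-only AEs: at Visits 5-7 of Tables 8-1 and 8-2 the remote check-in is S but the AE row is X. Protocol 12.5.1 does not define the end of the on-treatment period. SAP 2.7.1 uses a different, open-ended period, while SAP Section 4 reports no change to the protocol's analyses. If post-EOS events are meant to be left out, neither document says so.

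A reader might infer three stronger things that the documents do not support:

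- That these AEs can never reach the database. Section 8 removes the duty to enter S items but does not forbid entry. Unscheduled visits are X, and AEs up to EOS are entered at EOS. Participants who stop drug but stay in the study still have AEs collected (Section 9.1.1).
- That an off-treatment window is lost for everyone. That description does not fit completers in Cohorts 2-6. If the vaccine is taken as the treatment, 30 days after it have passed long before EOS for completers.
- That about 7% of AEs are lost. That figure is a share of time, and the documents give no AE rate.

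**Conclusion.** The point holds in a limited form and is minor. The row marking is certain in all six tables. The consequence is confined to the 30 days between EOS and the safety contact, and to three kinds of information: non-serious AEs first found then, updates obtained then, and the database copy of SAEs found then.

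Its reach differs by group. For Cohort 1 completers it is about 12 to 22 of the 30 required post-dose days, given the dosing intervals assumed. For early leavers it is the whole of the planned post-EOS follow-up. For other completers it is follow-up that the plan schedules but has not tied to a last dose.

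The effect on the AE tables rests on the SAP's open-ended definition; under protocol 12.5.1 some of these events might be excluded anyway. The number of events affected cannot be estimated from the documents. The immune response analyses, their confidence intervals and the sample size are untouched.

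**What to change.** Two changes belong together.

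1. In Tables 8-1 to 8-6, change S to X in the AE/SAE row at the safety contact (Day 412 or 419).
2. In protocol Section 12.5.1 and SAP Section 2.7.1, state one AE reporting period with one end date that includes this contact. Without this the newly entered events could still be left out under the on-treatment wording.

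If leaving out post-EOS non-serious AEs is intended, the alternative is to keep the S, state the cut-off in both documents, and reconcile it with Section 10.1.1.

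The cost is a small data-entry burden at sites, for information that staff already ask for and write in source. Concomitant medications and relapses at this contact would remain source-only unless their rows are changed too.
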